## 5.2 STUDY DRUG ADMINISTRATION

All eligible subjects will be treated with ibrutinib and venetoclax and rituximab. Each cycle is 28-days in length.

Venetoclax: Dose escalation administered daily orally for up to a total of 24 cycles. Each cohort will get assigned daily dose (from C1D2).

Ibrutinib: 560 mg (4 capsules) orally administered daily for up to a total of 24 cycles (from C1D2).

Rituximab: 375 mg/m^2 IV per package insert. Rituximab will be administered IV per institutional standards. weekly X 4 (Cycle 1); once on Day 1 of cycles 2-6 only, then every other cycle until Cycle 24 (total 18 doses of Rituxan from C1D1). Commercially available rituximab IV will be used.

## 6. TREATMENT PLAN

Study Type: Interventional

Study Design: Endpoint Classification: Safety/Efficacy Study

Intervention Model: Single Group Assignment, non-randomized design

Masking: Open Label

Population: The patient population consists of adult subjects  $>18$  years old with r/r DLBCL. The investigator or designee will complete a subject-screening log to document subjects considered for enrollment.

Description: Phase Ib, open-label single group dose finding study of ibrutinib, venetoclax and rituximab in relapsed or refractory DLBCL

## Study Design

Description: A dose-escalation will first determine the MTD and/or RPII of Bruton's Tyrosine Kinase (BTK) Inhibitor, Ibrutinib (PCI-32765) plus venetoclax and rituximab in relapsed or refractory DLBCL / Dose level and escalation described below

No of Pts	Dose Level	Ibrutinib a mg PO daily	Venetoclax b mg PO daily	Rituximab c mg/m  IV Day 1
	-1	560	200	375
3	1	560	400	375
3	2	560	800	375

a. Ibrutinib will be administered orally daily beginning Cycle 1 Day 2 for 24 cycles

b. Venetoclax is being administered orally daily, continuously beginning Cycle 1 Day 2 for 24 cycles

c. Rituximab will be administered IV per institutional standards; weekly X 4 (Cycle 1); once on Day 1 of cycles 2-6 only, then every other cycle until Cycle 24 (total 18 doses of Rituxan from C1D1)

Total number of patients: 30

Total Number of Centers: One center

## Sample Size

Justification: The MTD will be determined in a standard fashion using 3–6 patients per dose level. No more than 2 dose levels will be used in order to find the MTD. As such, for the phase I escalation portion of the study, no more than 12 patients will be required. Also we plan an expansion cohort at the MTD to examine the efficacy of the combination. We plan an expansion cohort with a maximum of 24 patients. Between the dose-escalation and dose-expansion, the maximum number of subjects will be 30.

Subjects with relapsed / refractory DLBCL that decide to participate on this study will sign consent and enter a screening period of 28 days. Patients that fulfill and maintain eligibility criteria will start cycle 1 day 1 treatment by receiving *Rituximab*. *Ibrutinib and venetoclax* will be administered daily starting on cycle 1 day 2. Follow up will be weekly during Cycle 1, on days 1 and 15 of cycles 2 and 3, then follow up monthly until disease progression, unacceptable toxicity or withdraw of consent.

## Restaging/ Length

### Of Therapy:

- Repeat cycles every 28 days for a total of 6 cycles. Patient may need to be evaluated in the office more frequently if needed at physician discretion
- Patient will be restaged after every 2 cycles of therapy. Patients, who are in at least stable disease with minimal drug toxicity after 2 cycles, will receive

subsequent treatment. Patients who have progression of the disease will be taken off study and complete post treatment follow up as described above

- Patients will receive 6 cycles then continue with venetoclax (daily) and ibrutinib (daily) with rituximab every other cycle until POD or toxicity or decision of stem cell transplantation if applicable (24 cycles max of treatment)
- Restaging will be every 2 cycles for the 1st 6 cycles and then every 3 cycles during treatment and disease follow up.

#### Post Treatment

- Follow Up: The post-treatment follow-up phase will begin once a subject discontinues ibrutinib, venetoclax and rituximab treatment and will continue a total of 36 months (from enrollment) has been reached or until death, lost to follow up, consent withdrawal, or study end, whichever occurs first. Subjects who discontinue for reasons other than disease progression (ie, for adverse event or Investigator decision), will complete an End-of-Treatment Visit ( $30 \pm 3$  days from the last dose of ibrutinib, venetoclax or rituximab, whichever is later), and must continue to have disease evaluations Q 3 months until disease progression, subject withdrawal, study is terminated or 36 months from enrollment has been reached.(12 weeks  $\pm 7$  days).
- Subjects who discontinue due to disease progression will complete an End-of-Treatment Visit and be followed for survival and subsequent anti-cancer therapy via phone call (12 weeks  $\pm 7$  days) until death or subject withdrawal or study is terminated.

## 7. **STUDY MEDICATION**

### 7.1 **VENETOCLAX**

#### 7.1.1 **Administration**

The first dose of venetoclax will be administered orally on Cycle 1 Day 2, of the Treatment Phase, after which venetoclax will be self-administered daily by the subjects on an outpatient basis. Venetoclax dosing will continue for up to a total of 24 cycles.

Patients will self-administer venetoclax tablets by mouth QD. Each dose of venetoclax will be taken with approximately 240 mL of water within 30 minutes after the completion of a low-fat breakfast. Examples of a low-fat breakfast include 2 slices of white toast with 1 tablespoon of low-fat margarine and 1 tablespoon of jam and 8 ounces/240 mL of skim milk (319 calories and 8.2 g fat) or 1 cup/30 g of cereal, 8 ounces/240 mL of skim milk, 1 slice of toast with jam, 1 cup/240 mL of apple juice, and 1 cup/240 mL of coffee or tea (520 calories and 2 g fat). If vomiting occurs within 15 minutes after taking venetoclax and all expelled tablets are still intact, another dose may

be provided. Otherwise, no replacement dose is to be given. In cases where a dose of venetoclax is missed or forgotten, the patient should take the dose as soon as possible, ensuring that the dose is taken with food within 8 hours after the missed dose. Otherwise, the dose should not be taken.

Patient compliance in taking the assigned daily dose of venetoclax will be assessed by standard pill counts. Bottles containing venetoclax tablets will be given to patients at regular scheduled visits. Previously distributed bottles will be returned to the clinic and tablets counted. Any discrepancy will be resolved with the patient at each clinic visit and documented in the patient record.

Guidelines for venetoclax dosage modification and treatment interruption or discontinuation are provided in Section 7.1.4.

### **7.1.2 Concomitant Therapies**

Concomitant therapy includes any prescription medications or over-the-counter preparations used by a patient between the 14 days preceding the study entry evaluation and the early study treatment termination visit/study treatment completion visit.

Patients who use oral contraceptives, hormone-replacement therapy, or other maintenance therapy should continue their use for the duration of the study for at least 3 months after the last dose of venetoclax and 12 months after the last dose of Rituximab.

Necessary supportive measures for optimal medical care will be given throughout the study according to institutional standards, including the use of growth factors (e.g., erythropoietin) if clinically indicated. Granulocyte colony-stimulating factor (G-CSF) may be administered as primary prophylaxis in each cycle of therapy, per the American Society of Clinical Oncology guidelines (Smith et al. 2006) or each site's institutional standards.

### **7.1.3 Prophylaxis and Management of Tumor Lysis Syndrome**

TLS is a risk for patients with NHL who are treated with high cell-killing agents, including venetoclax. Changes in blood chemistries consistent with TLS that require prompt management can occur as early as 6 to 8 hours following the first dose of venetoclax. The risk of TLS is a continuum based on multiple factors, including tumor burden and comorbidities. Risk is highest for those with bulky disease, elevated leukocyte count, elevated pretreatment LDH levels, compromised renal function, and dehydration. Perform tumor burden assessment with CT scan and CBC with WBC differential, assess blood chemistry (potassium, uric acid, phosphorus, calcium, and creatinine) in all patients and correct pre-existing chemistry abnormalities prior to initiation of treatment with venetoclax.

All patients must receive prophylaxis for TLS before the initiation of the first dose of venetoclax. Prophylaxis will include the following:

- Appropriate hydration, consisting of a fluid intake of approximately 2–3 L/day starting 24–48 hours before the start of treatment

- Administration of an agent to reduce uric acid (such as allopurinol 300 mg/day orally beginning 72 hours before dose and continuing for 3–7 days afterwards) or rasburicase IV (for those high risk patients with elevated uric acid levels before treatment, or when otherwise judged to be appropriate by the investigator) until normalization of serum uric acid and other laboratory evidence of TLS (e.g., elevated serum LDH levels).
- Laboratory results should be reviewed and electrolyte values should not demonstrate any clinically significant abnormalities before the first dose of venetoclax, or the patient should receive additional prophylactic treatment and hydration before the initiation of dosing.

On the day of the initial visit with administration of venetoclax (Cycle 1 Day 2), serial vital signs, serum chemistry, and hematology samples will be drawn before the dose of venetoclax and at 8 and 24 hours following the dose (see Appendix 1). These samples are to be sent STAT to the laboratory and the investigator or designee must review the results promptly. Laboratory values obtained before the dose of venetoclax are to be used to determine whether a patient developed a change related to TLS. Laboratory results of the 24-hour postdose must be reviewed before receiving the dose of venetoclax for that day. Patients who develop electrolyte changes suggestive of TLS should undergo aggressive management and further monitoring per Appendix 5, Recommendations for Initial Management of Electrolyte Imbalances and Prevention of Tumor Lysis Syndrome.

#### **Guidelines for hospitalization due to TLS risk**

Patients exhibiting specific characteristics at screening or initiation of venetoclax treatment are considered to be at high risk of developing TLS and must be hospitalized for more intensive prophylaxis and monitoring for the initial dose of venetoclax. These patients are identified by the presence of any of the following:

- any lymph mass  $\geq 10$  cm on the screening CT scan
- circulating lymphoma cells, defined by out of range (high) Absolute Lymphocyte Count (ALC) or the presence of abnormal cells in the peripheral blood differential signifying circulating lymphoma cells

In addition to characteristics requiring mandatory hospitalization, other patient characteristics may suggest an increased risk of TLS. These include, but are not limited to, the following:

- overall disease burden (e.g. several enlarged lymph nodes, even if none reaching 10 cm)
- elevated LDH levels
- compromised renal function, as evidenced by low creatinine clearance

- extensive bone marrow involvement
- Dehydration

Hospitalization is not mandatory for patients exhibiting these characteristics, but these and any other factors considered relevant to TLS should be considered in an overall assessment of the patient's state and their risk of TLS. Investigators should use their judgment in assessing TLS risk for their patients and may optionally hospitalize any patient they consider to be at risk for TLS for the first dose of venetoclax, with approval of the medical monitor.

### **Hospitalization Procedures**

For pts requiring hospitalization, hospitalization will begin the evening before the first dose of venetoclax and continue for 24 hours after. Upon admission, serum chemistry and hematology laboratory samples should be drawn and IV hydration should be started with a target of 150–200 cc/hr or as clinically appropriate. Laboratory results should be reviewed, and electrolyte values should not demonstrate clinically significant abnormalities before the first dose of venetoclax; otherwise, the patient should receive additional prophylactic treatment and hydration before the initiation of dosing. A nephrology (or acute dialysis) service must be consulted/contacted on hospital admission (per institutional standards) to ensure emergency dialysis is available and the appropriate staff is aware and prepared to handle any necessary intervention for TLS. Telemetry should also be considered.

Serial vital signs and TLS laboratory samples will be drawn before the first dose of venetoclax and at 8-, 12-, and 24-hour postdose; additionally, hematology samples will be drawn at 8- and 24-hour postdose (see Appendix 1). These samples are to be sent STAT to the laboratory and the investigator or designee must review the results promptly. Laboratory values obtained before the dose of venetoclax are to be used to determine whether a patient developed a change related to TLS. Laboratory results of the 24-hour postdose must be reviewed before receiving the dose of venetoclax for that day. Patients who develop electrolyte changes suggestive of TLS should undergo aggressive management and further monitoring per Appendix 5, Recommendations for Initial Management of Electrolyte Imbalances and Prevention of Tumor Lysis Syndrome.

Patients felt by the investigator to have particularly high risk of TLS may, in addition to hospitalization, start at a lower dose of venetoclax at the investigator's discretion, following discussion with the medical monitor.

- 

#### **7.1.4 Guidelines for Dosage Modification and Treatment Interruption or Discontinuation**

AE Attribution to study drugs will be assessed based on IB known data; for those not reported in the IB, relationship assessment will be at PI discretion to analyze.

**Table 1 Dose Modifications for Hematologic Toxicity Venetoclax Monotherapy**

Hematologic Toxicity	
Event(s)	Dose Delay or Modification
Grade 3 or 4 neutropenia, without infection or fever, and/or Grade 3 or 4 thrombocytopenia, first episode	

• Hold venetoclax.

• When counts recover to <math>\leq</math> Grade 2, resume previous doses of venetoclax.

• Administer G-CSF or growth factors for neutropenia as indicated.

• If the patient was not previously receiving prophylactic G-CSF, initiate prophylactic G-CSF for neutropenia as indicated.

Grade 3 or 4 neutropenia with infection and/or fever, first episode	

• Begin anti-viral medication and hold venetoclax until fever and/or infection resolves.

• Administer G-CSF or growth factors for neutropenia as indicated.

• When counts recover to <math>\leq</math> Grade 2 and infection has been fully treated, resume previous doses of venetoclax.

• If the patient was not previously receiving prophylactic G-CSF, initiate prophylactic G-CSF for neutropenia as indicated.

Recurrent Grade 3 or 4 neutropenia with/without fever and infection despite G-CSF	

• Hold venetoclax for at least 7 days.

• Administer G-CSF or growth factors for neutropenia as indicated.

• When counts recover to <math>\leq</math> Grade 2 and/or platelets are <math>\geq 75 \times 10^9/L</math>, resume venetoclax at one dose level reduction (see Table 3).

Grade 4 thrombocytopenia and/or symptomatic bleeding	

• Hold venetoclax for Grade 4 thrombocytopenia (platelets <math>< 25,000/\mu L</math>) or presence of symptomatic bleeding until resolution of bleeding.

• Platelets may be transfused at the discretion of the investigator.

• When platelet level rises to <math>\leq</math> Grade 2 without transfusional support for 5 consecutive days, restart venetoclax.

• For a second episode of severe thrombocytopenia and/or symptomatic bleeding, hold venetoclax. When platelet level rises to <math>\leq</math> Grade 2 without transfusional support for 5 consecutive days, restart venetoclax at one dose level reduction (see Table 3).

• For subsequent episodes of severe thrombocytopenia, hold venetoclax. When platelet level rises to <math>\leq</math> Grade 2 without transfusional support for 5 consecutive days, restart venetoclax at one dose level reduction.

G-CSF = granulocyte colony-stimulating factor.

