### 7.1.5 Infections Prophylaxis

All patients will be monitored closely for infection and treated aggressively according to institutional guidelines. If clearly indicated, anti-infective prophylaxis should be implemented at the investigator's discretion, including appropriate prophylaxis for viral, fungal, bacterial, or pneumocystis infections.

Although there is a potential for drug-drug interactions, there is likely to be limited potential clinical effects. There will be careful monitoring by the PI in such cases.

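### Table 1 tells staff to start an anti-viral at any first Grade 3-4 neutropenia with infection or fever, with no stated indication (minor wording correction)

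*Combined protocol and SAP*

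**What the plan says.** The row of Table 1 (Section 7.1.4) at issue is triggered by "Grade 3 or 4 neutropenia with infection and/or fever, first episode". Its instructions are:

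- On infection treatment and the venetoclax hold: "Begin anti-viral medication and hold venetoclax until fever and/or infection resolves".
- On growth factors: "Administer G-CSF or growth factors for neutropenia as indicated". A further bullet on prophylactic G-CSF is also limited to use as indicated.
- On restarting, once counts have recovered to Grade 2 or better and the "infection has been fully treated, resume previous doses of venetoclax".

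Two other sections govern infection and supportive care in general. Section 7.1.5 states: "All patients will be monitored closely for infection and treated aggressively according to institutional guidelines". It then allows prophylaxis where clearly indicated and at the investigator's discretion, "including appropriate prophylaxis for viral, fungal, bacterial, or pneumocystis infections". Section 7.1.2 states: "Necessary supportive measures for optimal medical care will be given throughout the study according to institutional standards". Neither section refers to the Table 1 row.

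**The concern.** The trigger is broad and the anti-viral instruction has no qualifier. The row does not require a viral infection to be suspected, let alone confirmed, and fever with no identified infection is enough. It names no other anti-infective and asks for no work-up. Nothing in the protocol explains why this one class was chosen.

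What is at stake is patient care, on a small scale. A site that follows the row to the letter gives an anti-viral to patients for whom the protocol states no reason to give one. A site that sensibly omits it departs from the written text. Nor is an anti-viral treated elsewhere as a neutral default: Section 8.1.1 permits hepatitis prophylaxis only if no contraindicated antiviral is used.

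**Working it through.** The plan states no figure on this point, so there is none to reproduce. The check is a comparison of texts.

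**Step 1: trigger against action.** The trigger names no organism and accepts infection, fever or both. The action names one drug class. The trigger therefore covers bacterial infection, fungal infection and unexplained fever, and in none of these does the row give a reason for an anti-viral.

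**Step 2: the row against itself.** The restart condition requires infection of whatever type to be fully treated. The row thus expects infections in general, while its treatment instruction speaks of one class.

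**Step 3: the other supportive-treatment instructions in Table 1.**

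| Row | Growth factor | Platelet transfusion | Anti-viral |
|---|---|---|---|
| Neutropenia without infection or fever and/or thrombocytopenia, first episode | 2, both as indicated | – | – |
| Neutropenia with infection and/or fever, first episode | 2, both as indicated | – | 1, no condition |
| Recurrent neutropenia despite G-CSF | 1, as indicated | – | – |
| Grade 4 thrombocytopenia and/or bleeding | – | 1, discretionary | – |

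The platelet instruction reads "Platelets may be transfused at the discretion of the investigator". The total is 5 + 1 + 1 = 7 instructions. Six are conditional or discretionary, and the anti-viral instruction is the only one that is neither. The row for recurrent episodes, which also covers fever and infection, names no anti-infective at all.

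**Step 4: the other places that deal with infection.**

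- Section 1.2.5.3 speaks of anti-infective prophylaxis by standard of care.
- Section 1.2.5.4 (lymphopenia) speaks of anti-infective prophylaxis as clinically indicated, for viral, fungal, bacterial and *Pneumocystis* infection.
- Section 1.3.5.6 (ibrutinib) asks for monitoring and prompt evaluation of fever and infection, and names no drug class.
- Section 7.1.5 treats infection by institutional guidelines and makes prophylaxis conditional.
- Section 7.2.4.1 interrupts ibrutinib for Grade 3 or greater neutropenia with infection or fever, and names no anti-infective.

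None of these qualifies the Table 1 instruction or explains it. Where the protocol names a treatment category for infection in these sections, it uses the broad term anti-infective and attaches a condition or a standard of care.

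**Step 5: how many patients.** The documents give no rate for this event with venetoclax, ibrutinib and rituximab together. The nearest figures come from other regimens: febrile neutropenia as a serious event in 6.2% of subjects in the ibrutinib combination studies (Section 1.3.5.2) and in 6.9% with venetoclax plus bendamustine and rituximab (Study M12-630, Section 1.2.4). If either rate applied to the maximum of 30 patients:

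- 30 × 0.062 = 1.9
- 30 × 0.069 = 2.1

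That is about two patients, for illustration only. The row also counts infection without fever and does not require a serious event, and the regimen differs, so the true number could be higher.

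**The case against.** The strongest reply is that infection treatment is handled elsewhere. Section 7.1.4 is headed as guidelines, and the purpose of Table 1 is to say when venetoclax is held, resumed or reduced; that part of the row is clear. Section 7.1.5 is where infection care is set out, so it is no gap that Table 1 lists no antibacterial or antifungal drug. The restart rule also makes full treatment of the infection a condition of resuming. This stands, and it limits the harm. It does not remove the instruction: Section 7.1.5 permits further treatment but does not make the anti-viral conditional.

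It can also be said that viral infection is a recognised concern with these drugs. The protocol mentions viral prophylaxis (Section 1.2.5.4), progressive multifocal leukoencephalopathy with ibrutinib (Section 1.3.5.6) and hepatitis B reactivation around rituximab (Appendix 1, note f). That is fair, but none of these passages concerns an acute episode of neutropenia with fever, and none is cited for this row.

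A reader might infer three stronger things that the documents do not support:

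- **The row steers staff to the wrong drug class, or away from the right one.** The documents do not say which class is right for a neutropenic patient with fever or infection, and they do provide for other treatment. The supportable statement is that a class is named with no indication.
- **Six conditional instructions out of seven measures the harm.** The count shows inconsistent wording. It says nothing about patients affected or injury.
- **Anti-infective was certainly meant.** The usage elsewhere makes a slip plausible, but no text confirms it.

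**Conclusion.** The point holds as a minor patient-safety wording correction. The row gives an unconditional instruction to start an anti-viral on a trigger that includes non-viral infection and fever alone, and nothing in the protocol supplies the missing condition. The consequence is a possibly unneeded anti-viral at a patient's first such episode; no other treatment is withheld.

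The conclusion rests on reading the row as written and on the absence of any qualifying text in the sections compared. It needs no assumption about the event rate. The DLT definition, the MTD rule, the stopping boundaries and the analysis are unaffected. Whether the cause is a slip or an unexplained clinical choice is for the sponsor's clinicians to say.

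**What to change.** In that row of Table 1, replace the anti-viral phrase with *Begin anti-infective treatment as indicated per institutional guidelines (see Section 7.1.5)*, and leave the venetoclax hold as it is. If the sponsor's clinicians confirm that an anti-viral was meant, keep the class and add *if viral infection is suspected or confirmed*.

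The cost is one phrase in one row at the next amendment, with no added visits, data or patients.

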## **4. STUDY POPULATION**

### **4.1 INCLUSION CRITERIA**

Patients must meet the following criteria for study entry:

1. Eastern Cooperative Oncology Group Performance Status </= 2.
2. Histologically or cytologically confirmed diagnosis of advanced DLBCL.
3. Ability and willingness to comply with the requirements of the study protocol
4. Prior therapy: relapsed or refractory patients who have received one prior therapy are eligible. If treated with small molecule, washout therapy with a period of greater than 5x the half-life of the molecule. Patients who have previously received high-dose chemotherapy with peripheral stem cell support are eligible. Washout period of 21 days.
5. Presence of at least one lymph node evaluable or mass measurable for response.
6. Age greater than or equal to 18 years.
7. Recovery from any previous treatment therapy.
8. Laboratory parameters:
  - Absolute neutrophil count (ANC)  $\geq 1000/\text{mm}^3$  independent of growth factor support (unless the treating physician deems the neutropenia is related to bone marrow involvement, then an ANC of  $> 750/\text{mm}^3$  is allowed)
  - Platelets  $\geq 100,000/\text{mm}^3$  or  $\geq 50,000/\text{mm}^3$  if bone marrow involvement independent of transfusion support in either situation
  - Total bilirubin  $\leq 1.5 \times \text{ULN}$  unless bilirubin rise is due to Gilbert's syndrome or of non-hepatic origin
  - AST (SGOT) and ALT (SGPT)  $\leq 3 \times$  upper limit of normal (ULN)
  - Creatinine:  $\text{CrCl} \geq 50 \text{ ml/min}$  (calculated using Cockcroft-Gault Formula-Appendix 2)  
Prothrombin time (PT) or international normalized ratio and partial thromboplastin time (PTT) not to exceed 1.2 times the institution's normal range
9. Women of childbearing potential and men who are sexually active must be practicing a highly effective method of birth control during and after the study consistent with local regulations regarding the use of birth control methods for subjects participating in clinical trials. Men must agree to not donate sperm during and after the study. For females, these restrictions apply for 3 months after Venetoclax and 12 months after Rituximab For males, these restrictions apply for 3 months after the last dose of study drug.
10. Women of childbearing potential must have a negative serum (beta-human chorionic gonadotropin [ $\beta$ -hCG]) or urine pregnancy test at Screening. Women who are pregnant or breastfeeding are ineligible for this study.

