**Table 2 Venetoclax Dose Modifications for Non-Hematologic Toxicity**

Non-hematologic Toxicity	
Event(s)	Dose Delay or Modification
Grade 3 or 4 TLS (first episode and subsequent episodes)	

Hold all study treatments (venetoclax) until TLS resolves. The patient's next dose may be delayed for up to 28 days.

Following complete resolution of TLS, if venetoclax was held for 14 days or less, venetoclax may be restarted at the same dose or at one lower dose level as determined by the investigator based on a risk assessment (including tumor burden status) in conjunction with prophylactic hydration and uricosuric agent; hospitalization for restarting the venetoclax dose may be considered at the discretion of the investigator. Dose must be resumed at one lower dose level if interruption lasted more than 14 days.

Grade 3 or 4 non-hematologic toxicity not specifically described above	

Delay venetoclax for a maximum of 28 days.

First episode: If improvement to Grade <math>\leq</math> 1 or baseline, resume previous doses of venetoclax.

For subsequent episodes: If improvement to Grade <math>\leq</math> 1 or baseline, restart venetoclax at one dose level reduction (see Table 3).

Grade 2 non-hematologic toxicity	Delay treatment with venetoclax until resolution to Grade $\leq$ 1 (or baseline status) for a maximum of 28 days. After resolution, resume the full dose of venetoclax.
Grade 1 non-hematologic toxicity	No dose reduction or delay

TLS = tumor lysis syndrome.

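### Read literally, Table 1's recurrent-neutropenia row lets venetoclax restart on the platelet count alone while neutrophils are still Grade 3 or 4

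*Combined protocol and SAP*

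**What the plan says.** Section 7.1.4, Table 1, has three rows that deal with neutropenia.

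- **First episode, no fever or infection.** The trigger is "Grade 3 or 4 neutropenia, without infection or fever, and/or Grade 3 or 4 thrombocytopenia, first episode". Venetoclax is held and goes back to the previous dose once counts are Grade 2 or lower.
- **First episode with infection or fever.** Venetoclax is held until counts are at or below "Grade 2 and infection has been fully treated, resume previous doses of venetoclax".
- **Recurrence.** The trigger is "Recurrent Grade 3 or 4 neutropenia with/without fever and infection despite G-CSF". Venetoclax is held for at least 7 days, G-CSF is given as indicated, and treatment resumes one dose level lower when counts are at or below "Grade 2 and/or platelets are" at least 75 × 10⁹/L.

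Table 3 sets the lower level: 800 mg becomes 400 mg, and 400 mg becomes 200 mg. Section 5.1 gives the neutrophil thresholds: Grade 3 is an ANC below 1,000/mm³ and Grade 4 is below 500/mm³.

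A separate Table 1 row covers Grade 4 thrombocytopenia or symptomatic bleeding. There, "Platelets may be transfused at the discretion of the investigator", and restart requires platelets at or below "Grade 2 without transfusional support for 5 consecutive days, restart venetoclax".

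**The concern.** The recurrent event is the worse one, because the neutropenia has come back in spite of growth factor. One would expect its restart test to be at least as strict as the test after a first episode. As worded it is weaker. The *or* branch asks only about platelets, although the row is triggered by neutrophils.

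In isolated neutropenia the platelet condition may already be met when the event starts. The rule then reduces to a 7-day wait and a dose step, with no check that neutrophils have recovered. Venetoclax could restart at 400 mg or 200 mg during severe neutropenia, and a clinician who did this would be following the protocol.

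What is at stake is the safety of the patients who reach this row. No estimate, error rate or sample size depends on it.

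**Working it through.** The plan gives no figure to reproduce. The check is a comparison of conditions, with one small piece of arithmetic.

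**Step 1: truth table for the recurrent row.** Let A mean counts at Grade 2 or lower and B mean platelets of at least 75 × 10⁹/L. *And/or* is read as an inclusive *or*.

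| A | B | As written | With *and* |
|---|---|---|---|
| yes | yes | restart | restart |
| yes | no | restart | hold |
| no | yes | restart | hold |
| no | no | hold | hold |

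The third line is the problem.

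**Step 2: one blood count put through each neutropenia row.** Take an ANC of 400/mm³ and platelets of 80 × 10⁹/L after a 7-day hold. Since 400 < 500, the neutropenia is Grade 4 and A fails. Since 80 ≥ 75, B is met.

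- First episode, either row: A is required, so hold.
- Recurrence: B is enough, so restart one level lower.

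The same count therefore holds the drug after a first episode and releases it after a second.

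**Step 3: can the platelet condition be met at onset?** Section 4.1, criterion 8, sets an entry minimum of 100,000/mm³, or 50,000/mm³ "if bone marrow involvement independent of transfusion support in either situation". A patient at the general minimum has a margin of (100 − 75)/100 = 25% before B fails. A patient admitted at the marrow-involvement minimum is already below 75. So B may hold at onset in isolated neutropenia. Entry values do not show how often it would hold during recurrent myelosuppression. In the venetoclax plus bendamustine-rituximab study (Section 1.2.4, Study M12-630), 46.6% of patients had thrombocytopenia, and it was Grade 3 or above in 20.7%.

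**Step 4: does another rule supply the neutrophil test?**

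- Table 2 concerns non-hematologic toxicity only. At Grade 2 it says "Delay treatment with venetoclax until resolution to Grade" 1 or lower, or baseline. With Section 7.1.5 on treating infection, this covers most of what the recurrent row leaves out about infection, but it does not cover ANC.
- Section 7.2.4.1 stops ibrutinib for Grade 4 hematologic toxicity, or for neutropenia of at least Grade 3 with infection or fever, until Grade 1 or baseline. It governs ibrutinib, not venetoclax. Grade 3 neutropenia without fever or infection does not trigger it.
- Sections 9 and 9.1 allow discontinuation for unacceptable adverse events, for drug-related laboratory abnormalities that persist, and when the investigator judges continuation unsafe. These are grounds for stopping, not conditions for restarting.

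None of these requires neutrophil recovery before venetoclax resumes after a recurrence.

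**The case against.** The best defence is that the hazardous reading is not the natural one. The row is about neutropenia, so the counts that must recover are most naturally the neutrophils, and the platelet clause would apply when platelets have also dropped. The first row uses *and/or* in that loose way to join neutropenia and thrombocytopenia. The literal reading also nearly defeats itself: a patient restarted with Grade 3 or 4 neutrophils is still in the state for which the row orders a hold. On this view the text is careless rather than dangerous.

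Most of that stands as an account of intent. It does not change what the row permits, and the term for counts is not defined. A dosing table should not need its reader to override it.

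The safeguards also carry weight. The minimum hold, the dose step, the investigator's judgement and the discontinuation criteria all narrow the practical risk. So do the ibrutinib rules, especially for Grade 4 or febrile cases, where repeated occurrences end in ibrutinib discontinuation and so in the end of the Treatment Phase. They make an unsafe restart less likely without supplying the missing test.

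A reader might also see a serious conflict in the platelet rules, because a first Grade 4 thrombocytopenia fits both the first row and the Grade 4 row. A transfused count could pass the former and fail the latter. The documents do not support treating this as more than a tidy-up: the Grade 4 row is the more specific and the stricter, and following it satisfies both.

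**Conclusion.** The point holds as a minor patient-safety wording correction. As written, the recurrent-neutropenia row accepts platelets of at least 75 × 10⁹/L in place of neutrophil recovery. It is weaker than either first-episode row, and nothing else in the plan sets a neutrophil condition for that restart. The conclusion rests on reading *and/or* as an inclusive *or*. It does not assume that the authors meant it or that investigators would act on it.

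Two stronger claims are tempting and should not be made.

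- **That the platelet condition is usually met by default.** Entry minima do not establish platelet counts during recurrent toxicity on three drugs. The thrombocytopenia rates in Study M12-630 and the lower entry limit for marrow involvement point the other way for some patients.
- **That the number affected can be calculated.** Single-agent rates of Grade 3 or higher neutropenia (12.3% with venetoclax, Section 1.2.4; 23% with ibrutinib, Section 1.3.5.7) give 30 × 0.123 = 3.7 and 30 × 0.23 = 6.9 patients with any such event. Getting from there to patients at risk needs the share who recur despite G-CSF, the share still unrecovered after 7 days with adequate platelets, and the share restarted anyway. The documents give none of these, and the regimen is a triplet.

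**What to change.** Reword the recurrent-neutropenia row along these lines:

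> Hold venetoclax for 7 days or longer. Resume one dose level lower (Table 3) once neutrophils are Grade 2 or lower and any infection has been fully treated. If platelets also fell, additionally require platelets of at least 75 × 10⁹/L, or a return to baseline for patients enrolled below that level because of marrow involvement.

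The infection clause brings the row into line with the febrile first-episode row. As an optional tidy-up, state that the Grade 4 thrombocytopenia row governs every Grade 4 or bleeding event, including the first, and leave its 5-day transfusion-free condition as it is.

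The cost is an amendment to table wording, with no added visits, tests or patients. Some venetoclax holds will be longer. Those most affected are patients enrolled with an ANC between 750 and 1,000/mm³ because of marrow involvement. They would have to rise above their entry level to restart, as the first-episode rows already require.
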